1. INTRODUCTION

Ospemifene is indicated for post-menopausal women diagnosed with vulvar vaginal atrophy (VVA) and dyspareunia. While ospemifene clinically significantly reduces pain associated with dyspareunia, there has been little prospective documentation using vulvoscopy with detailed photography of the visible changes to the vulva, vestibule and vaginal region with daily administration of 60 mg ospemifene in post-menopausal women with VVA and dyspareunia. This study will include a total of 6 prospective photographic sessions of the vulva, vestibule and vagina over the 20 weeks administration of 60 mg ospemifene in the study. Comparisons will be made of baseline photography (vulvoscopy session 0) with photography at 4 weeks (vulvoscopy session 1), 8 weeks (vulvoscopy session 2), 12 weeks (vulvoscopy session 3), 16 weeks (vulvoscopy session 4) and 20 weeks (vulvoscopy session 5).

2. TRIAL OBJECTIVE

The primary objective of this study is to prospectively document, using vulvoscopy with detailed photography, the visible changes to the vulva, vestibule and vaginal region in post-menopausal women with dyspareunia taking 60 mg daily ospemifene for twenty weeks at 6 timepoints: baseline, 4 weeks, 8 weeks, 12 weeks, 16 weeks and 20 weeks.

Secondary objectives include changes in pain as noted on the pain scale (appendix 2) and the q-tip test, in the vestibule on visual scale (appendix 3) by the clinician and sexual function by subject diary (appendix 4).

3. DESCRIPTION OF RESEARCH DESIGN

3.1 Overall Study Plan

This is an unblinded study to be conducted at a single research center, San Diego Sexual Medicine. Subjects meeting inclusion and exclusion criteria will receive 60 mg ospemifene daily for twenty weeks. After the informed consent is

signed, a baseline physical examination, and vulvoscopy with detailed photography of the vulva, vestibule and vagina, will be performed. Physical examination and vulvoscopy with detailed photography of the vulva, vestibule and vagina, will be repeated prospectively every 4 weeks for a total of 20 weeks. Therefore, physical examination and vulvoscopy with detailed photography of the vulva, vestibule and vagina will be performed prospectively at baseline (vulvoscopy session 1), 4 weeks (vulvoscopy session 2), 8 weeks (vulvoscopy session 3), 12, weeks (vulvoscopy session 4), 16 weeks (vulvoscopy session 5) and 20 weeks (vulvoscopy session 6) following daily administration of 60 mg ospemifene.

3.2 Study Duration

Each eligible subject will participate in the study for approximately 20 weeks. It is expected this single site investigator-initiated research study will be completed approximately 8 months following initial approval by the Independent Review Board.

3.3 Independent Review Board (IRB) Approval

Prior to conducting any study-related procedures, the Principal Investigator will obtain written approval from Aspire Independent Review Board for the informed consent form, protocol, recruitment materials, and any written information provided to Subjects pertaining to the procedure.

3.4 Rationale for Study Design and Subject Selection

Currently there have been limited prospective studies using vulvoscopy with detailed photography demonstrating visible changes to the vulva, vestibule and vagina following oral administration of 60 mg ospemifene in post-menopausal women with VVA and dyspareunia. Information regarding visible changes to the vulva, vestibule and vagina may be very important to the patient and to the health care provider to best understand the beneficial effects of ospemifene and to ensure patient compliance with treatment.

This study is being conducted in an unblinded fashion because the primary endpoint is a collection of photographs. All subjects will receive the same active drug at the same dosage.

4. Selection and Withdrawal of Subjects

The study population will include menopausal females with vulvar vaginal atrophy (VVA) causing dyspareunia.

4.1 Subject Inclusion Criteria

All criteria below must be met in order for a Subject to be eligible for study participation.

1. Subject provides written informed consent and HIPAA authorization before any study procedures are conducted;

2. Subject is female;
3. Subject is aged 21-80 years;
4. Subject has a body mass index (BMI) < 37 kg/m²
5. Subject is menopausal either naturally (at least 12 months amenorrheic) or 6 weeks after a bilateral salpingo-oophorectomy prior to natural menopause; subjects with hysterectomy only must have a serum FSH > 40 mIU/mL;
6. Subject has vulvovaginal atrophy with dyspareunia;
Subject agrees to comply with the study procedures and visits.

4.2 Subject Exclusion Criteria

Subjects who meet any of the following criteria shall be excluded:

1. Subject has a hypersensitivity to any of the ingredients of ospemifene;
2. Subject has used ospemifene in the past;
3. Subject has documented or suspected breast cancer, history of heart attack or stroke;
4. Subject has clinically significant findings on physical examination;
5. Subject has uncontrolled hypertension;
6. Subject has any chronic medical condition or psychologic disorder that the Principal Investigator feels makes her ineligible for the study;
7. Subject is currently on local or systemic androgen therapy including local or systemic testosterone (washout 14 days for local or topical androgen or non-depot injection, 1 month for depot, 6 months for pellet);
8. Subject is currently on local or systemic estrogen therapy or androgen therapy (washout 14 days for vaginal estrogen, 60 days for oral/transdermal therapy);
9. Subject is currently using a SERM or products that have estrogenic or anti-estrogenic effects within last month;
10. Subject currently using itraconazole, ketoconazole, digitalis or alkaloids heparin or strong cytochrome P 450 3A4 inhibitors;
11. Subject has a history of substance abuse within 12 months prior, or consuming > 14 alcoholic drinks per week;
12. Subject has received an investigational drug within 30 days prior to signing consent;
13. Subject has any condition or exhibits behavior that indicates to the Principal Investigator that the Subject is unlikely to be compliant with study procedures and visits.

4.3 Subject Withdrawal Criteria

The Principal Investigator may discontinue a subject's participation in the study at any time if it is considered in the subject's best interest to do so. Such a decision may be precipitated by adverse events, new onset illness, clinically important changes in vital signs, physical examinations, or laboratory tests. Subjects who

are noncompliant with study procedures and visits may also be withdrawn by the Principal Investigator.

Subjects may withdraw from participation in the study at any time for any reason. A subject's decision to withdraw will not cause the subject to lose any benefits to which she is entitled. A subject who withdraws prematurely from the study will return to the clinic as soon as possible and before any further ospemifene treatment of any kind, to undergo the final visit evaluations.

If a subject prematurely withdraws or is withdrawn from study participation, the reason for the withdrawal must be recorded on the case report form (CRF). Record the primary reason for premature withdrawal according to the following categories:

- **Adverse Event:** Subject experiences an intolerable event, which may or may not be related to the study medication;
- **Withdrawn Consent:** Subject withdraws from study participation for personal reasons (exclude adverse experience before indicating this category);
- **Concomitant Medication Violation:** Subject initiates, discontinues, or changes dosing regimen of concomitant medication in violation of the protocol, which, in the judgment of the Principal Investigator, may adversely affect evaluation of safety;
- **Lost-to-Follow-up:** Subject does not return for evaluation and no further contact is made by the Subject after three documented phone or email attempts and a final attempt by certified mail.
- **Other:** Any reason that does not fit in the above 4 categories: the reason will also be recorded on the CRF.

5. Clinical Procedures

Clinical procedures throughout the study are described in the sections below, and summarized briefly in **Appendix 1**.

5.1 Informed Consent and HIPAA

Each potential study Subject must provide written informed consent and authorize release of her protected health information before any study procedure is conducted.

5.1.1 Informed Consent

An Informed Consent Form (ICF) and California Bill of Rights will be written in accordance with established criteria of the Aspire IRB and the appropriate federal regulations to describe the study plan, procedures, and risks. The Aspire IRB must approve the ICF and any ICF amendments or administrative revisions before they are used.

Potential subjects will be informed of the study plan and schedule and will provide written informed consent prior to the initiation of any study-related procedures. Each subject will be afforded the opportunity to ask any questions about the study plan, procedures, or possible risks. The date the consent form was signed by the subject and the Principal Investigator or his designee will be documented. The screening procedures will be performed and recorded on the source documents. No screening procedures may be initiated prior to the Subject signing the ICF.

The original, signed ICF will be retained in the Principal Investigator's study files. A copy of the signed and dated consent form will be given to each potential Subject.

5.1.2 HIPAA

In accordance with the Health Insurance Portability and Accountability Act (HIPAA) Privacy Rule, the Subject has the right to determine who has access to protected health information.

Potential subjects will provide written authorization for the Principal Investigator to access the subject's personal health information (PHI) for the purposes of the study. Personal health information relevant to the study includes medical records and the results of tests and procedures. The subject's written authorization also allows sharing this information with the Food and Drug Administration (FDA), other regulatory agencies and the Aspire IRB. The Subject may cancel the authorization in writing at any time, but will then be withdrawn from the study.

An authorization form must include the following elements:

- A description of the information to be used or disclosed;
- Identification of the persons or class of persons authorized to make the disclosure(s);
- Identification of the persons or class of persons authorized to receive the PHI;
- A description of the purposes for the uses or disclosures;
- Expiration date or event triggering expiration;
- Individual's signature and date;
- A statement of the individual's right to revoke his/her authorization;
- A statement of consequences to the individual for refusing to sign the authorization;
- A statement of the potential for the information to be re-disclosed by recipients and no longer protected by the Privacy Rule; and
- If the individual will be denied access to records during the study, a statement that the Subject agrees to temporarily waive access to records during the research.

The original, signed HIPAA authorization form will be retained in the Principal Investigator's study files. A copy of the signed and dated form will be given to each potential Subject.

5.2 Subject Screening (Visit 1)

Candidates for enrollment will be screened within 28 days prior to enrollment. Before initiation of any test procedures, Subjects will be fully informed of the study plan, procedures, and risks involved in participating in the study. Each potential Subject will be required to read and to indicate her understanding by signing and dating the ICF prior to initiation of any screening procedures.

The site will maintain an ongoing screening log of all subjects who provide written informed consent. The screening log will include each Subject's initials, date of birth, and screening number (assigned sequentially), including reason for exclusion if the subject is determined to be ineligible for the study. If the subject does not have a middle name, a dash will be used instead of that initial (e.g., J-S). The subject will be identified on source documents by initials and the assigned Subject number.

Screening procedures will consist of the following:

- Medical history, including surgical procedures, tobacco, alcohol, and medication use (prescription and non-prescription drugs, nutritional supplements, herbals, or investigational drugs);
- Measurement of height (inches) and weight (pounds) in indoor clothing without shoes; recorded to the nearest whole unit;
- Vital signs (blood pressure, pulse, respiration rate, and oral temperature);
- Pain scale;
- Urinalysis;
- Clinical laboratory tests estradiol, LH, FSH (the same clinical laboratory will be used throughout the study);
- Physical examination including review of systems and breast and gynecologic exam;
- Vulvoscopy including detailed photograph(s) of the vulva, vestibule and vagina region and pain scale/Q-tip testing;
- Visual scale.

The Principal Investigator will review all screening assessments and sign and date all reports. Any clinically significant abnormalities will be indicated by the abbreviation CS on the report. Results that are not clinically significant will be identified as NCS. The Principal Investigator will review all inclusion and exclusion requirements and document the eligibility of each Subject to participate further.

5.3 Study Restrictions

The restrictions listed below will be applied from study drug administration through study termination. The Principal Investigator will determine if a deviation from the restrictions warrants Subject withdrawal from the study.

From screening through completion of the last study procedures, Subjects may not do the following:

- use of any prescription hormone (any administration);
- change any prescription medication without notifying the Principal Investigator;
- use any over-the-counter products, vitamins or herbal and/or nutritional supplements;
- use any investigational drug or medical device products;
- use any drugs of abuse.

5.4 Study Day 0 (Visit 2)

Subject meeting inclusion and exclusion criteria may enroll any time after screening up to 28 days after consent is signed:

- Measure vital signs (blood pressure, pulse, respiration rate, and oral temperature);
- Assess any change in concomitant medication since screening visit;
- Complete pain scale;
- Vulvoscopy including detailed photograph(s) of the vulva, vestibule and vagina region and pain scale/Q-tip testing;
- Complete visual scale;
- Educate subject as to how study medication is administered (taken each morning);
- Dispense study medication (35 tabs), diaries (10) and lubricant;
- Assess adverse events.

5.5 Study Days 28 ± 7, 56 ± 7, 84 ± 7, 112 ± 7 (Visits 3, 4, 5, 6)

Each Subject will report to the Principal Investigator's office on study Days 28, 56, 84 and 112 ± 7 for the following procedures at each visit:

- Measure vital signs (blood pressure, pulse, respiration rate, and oral temperature);
- Assess any change in concomitant medication;
- Complete pain scale;
- Vulvoscopy including photograph(s) of the vulvar vestibule region and pain scale/Q-tip testing;
- Complete visual scale;

- Collect medication and calculate compliance (reeducate Subject on medication administration if compliance is <80% or >120%);
- Collect diaries;
- Dispense study medication (35 tabs), new diaries and new lubricant;
- Assess adverse events.

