5.6 Study Day 140 ± 7 (Visit 7) or Early Termination Visit

On Study Day 140 ± 7 each Subject will report to the Principal Investigator's office for the following procedures:

- Measure vital signs (blood pressure, pulse, respiration rate, and oral temperature);
- Assess any change in concomitant medication;
- Complete pain scale;
- Perform physical examination including review of systems and breast and gynecologic exam;
- Vulvoscopy including photograph(s) of the vulva, vestibule and vagina region and pain scale/Q-tip testing;
- Complete visual scale;
- Collect medication and calculate compliance;
- Collect diaries;
- Assess adverse events.

If a Subject terminates study participation or is withdrawn from the study by the Principal Investigator before visit 7, the Subject should return to the Principal Investigator's office as soon as possible for the following procedures:

- Measure vital signs (blood pressure, pulse, respiration rate, and oral temperature);
- Assess any change in concomitant medication;
- Complete pain scale;
- Assess any change in concomitant medication since screening visit;
- Perform physical examination including review of systems and breast and gynecologic exam;
- Vulvoscopy including photograph(s) of the vulva, vestibule and vagina region and pain scale/Q-tip testing;
- Complete visual scale;
- Collect medication and calculate compliance;
- Collect diaries;
- Assess adverse events.

6 Adverse Event Assessment

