7.1 Study Medication

Ospemifene (Osphena[®]) 60 mg tablets will be provided by Shionogi Pharmaceuticals, in sufficient quantity to dose all Subjects.

The ospemifene tablets provided for this study will be taken from commercial drug supply.

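### Thirty-five tablets per visit do not cover the 42 days that the visit windows allow between visits, and the undefined compliance check would not identify the resulting run-out (minor)

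*Protocol*

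**What the plan says.** Protocol section 3.1 sets the regimen: "Subjects meeting inclusion and exclusion criteria will receive 60 mg ospemifene daily for twenty weeks". Section 7.1 supplies 60 mg tablets, so use is one tablet a day.

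Section 5.4 (Day 0, Visit 2) has the site "Dispense study medication (35 tabs), diaries (10) and lubricant". Section 5.5 repeats the quantity at Visits 3 to 6: "Dispense study medication (35 tabs), new diaries and new lubricant".

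Visit timing is tied to study day, not to the previous visit. Visits 3 to 6 fall "on study Days 28, 56, 84 and 112 ± 7 for the following procedures at each visit", and section 5.6 says of Visit 7: "On Study Day 140 ± 7 each Subject will report to the Principal Investigator's office for the following procedures".

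Medication is collected and compliance calculated at Visits 3 to 7 (sections 5.5 and 5.6; Appendix 1 has a row for collecting and reconciling medication). At Visits 3 to 6 the site must "reeducate Subject on medication administration if compliance is <80% or >120" per cent. Section 5.6 gives no threshold for Visit 7. No formula for compliance is given anywhere.

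No passage says that collected tablets are re-issued, that the quantity is matched to the next appointment, or that the spacing between visits has an upper limit.

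**The concern.** The quantity and the windows do not fit each other. Thirty-five tablets are enough for a visit held on its nominal day followed by one held 7 days late. They are not enough for an early visit followed by a late one, although both are within the protocol's windows.

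Any days without drug come at the end of the interval, immediately before the next photographs, visual scale and Q-tip test. The primary objective (section 2) is to document changes under daily use, so an assessment after several untreated days is not quite the assessment that the plan describes. The compliance check is the only routine safeguard, and without a stated denominator it may not register the run-out, or may register it as something else.

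**Working it through.** **Inputs.** 35 tablets at each of Visits 2 to 6 (sections 5.4, 5.5); one tablet a day (sections 3.1, 7.1); nominal days 0, 28, 56, 84, 112 and 140, with ±7 from Day 28 on (sections 5.5, 5.6; Appendix 1); re-education below 80% or above 120% at Visits 3 to 6 (section 5.5).

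**The plan's own figure.** 28 + 7 = 35. The quantity equals one nominal interval plus one late window.

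**Longest permitted interval** = (next nominal day + 7) − (previous nominal day − 7), with Day 0 fixed.

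| Interval | Longest, days | Tablets | Shortfall |
|---|---|---|---|
| Visit 2 to 3 | 35 − 0 = 35 | 35 | 0 |
| Visit 3 to 4 | 63 − 21 = 42 | 35 | 7 |
| Visit 4 to 5 | 91 − 49 = 42 | 35 | 7 |
| Visit 5 to 6 | 119 − 77 = 42 | 35 | 7 |
| Visit 6 to 7 | 147 − 105 = 42 | 35 | 7 |

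The shortfall can shift by a day depending on how visit-morning doses are counted.

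**Compliance of a woman who takes every tablet over 42 days**, by denominator:
- days elapsed: 35/42 = 83.3%, no flag;
- tablets dispensed: 35/35 = 100%, no flag;
- fixed 28 days: 35/28 = 125%, flagged, but as apparent over-use.

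On days elapsed, intervals of 36 to 42 days give 97.2% down to 83.3%. Falling below 80% would need more than 35/0.80 = 43.75 days, which the windows do not allow.

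**How often.** The documents give no distribution of visit timing, so two assumptions are shown, with visits independent of each other.

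*Uniform over the 15 days of each window.* The interval exceeds 35 days when the later offset minus the earlier offset is more than 7. The pairs giving 8 to 14 number 7 + 6 + 5 + 4 + 3 + 2 + 1 = 28 of 15 × 15 = 225, or 12.4%. The mean shortfall in those pairs is (7×1 + 6×2 + 5×3 + 4×4 + 3×5 + 2×6 + 1×7)/28 = 84/28 = 3 days. By simulation, 45% of women have at least one such interval among the four.

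*SD 3 days around the nominal day.* By simulation, about 4% of intervals and about 14% of women, with a mean shortfall of about 2 days. Re-simulation moves the 14% between 12% and 15%, depending on whether offsets beyond ±7 are excluded.

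**Which figure applies where.** The SAP's signed-rank tests compare baseline with study end, so the Visit 6 to 7 interval is the one directly before a tested assessment: 10 × 0.124 = 1.2 women (uniform) or 10 × 0.04 = 0.4 (SD 3) of the 10 planned. The 45% and 14% apply to the visit-by-visit tables in protocol sections 8.2 and 8.3.

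**Treatment lost per woman** over the four intervals: 4 × 0.124 × 3 = 1.5 days (uniform) or 4 × 0.04 × 2 = 0.3 days (SD 3), against 140 planned, about 1% or 0.2%.

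**If collected tablets were re-issued**, cumulative supply against the latest permitted day would be 35 for Day 35, 70 for Day 63, 105 for Day 91, 140 for Day 119 and 175 for Day 147. It never falls short.

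**The case against.** The strongest reply is that the problem rests on an assumption. If the site counts the tablets and hands them back, no permitted schedule runs short, and Appendix 1 speaks of reconciling as well as collecting. This stands as a limit: the documents are silent, and the shortfall is conditional. It does not settle the matter, because no passage provides for re-issue and a site following the text would collect and dispense 35.

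A reader might infer that the plan makes a gap inevitable. It does not. Earliness at one visit plus lateness at the next must exceed 7 days, and the first interval is exempt. The earliest previous visit plus 35 days always reaches the next nominal day (for example 21 + 35 = 56), so run-out can occur only when the next visit is late. For Visit 7 this means after Day 140, and the protocol does not say whether dosing continues up to a late Visit 7.

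A reader might also infer that the 80% and 120% limits cannot be reached. That is not so. Missed doses can bring compliance below 80% at any interval (22/28 = 79%), and 35/28 = 125% exceeds 120% at the nominal interval. Nor is the run-out invisible: sections 7.3 and 7.6 have dispensing dates recorded, so an empty return after 36 or more days can be found in the records. What is missing is a rule that looks for it.

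Finally, nothing in the documents shows that two or three untreated days change the photographs or swab pain. That objection stands. Diary data cover the whole interval (protocol section 8.3) or the 4 weeks before the visit (SAP), so they are only partly exposed.

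**Conclusion.** The inconsistency is real but minor. As written, four of the five intervals may outlast the dispensed tablets by up to 7 days. A fully adherent woman in that position is not flagged on a days-elapsed or tablets-dispensed basis, and is flagged for the wrong reason on a fixed 28-day basis. At Visit 7 there is no threshold at all.

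For the end-of-study tests this concerns about 12% of women under uniform timing (mean shortfall 3 days) or about 4% with SD 3 days (mean about 2 days). For the visit-by-visit tables, 45% or 14% of women would have at least one affected interval. These figures assume one tablet a day, independent visit timing and no re-issue of collected tablets.

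It would be tempting to conclude that the results understate the drug's effect, or that nearly half the women are affected at the tested endpoint. The documents support neither: the effect on outcomes cannot be sized from them, and the 45% counts all four later intervals under the wider of the two timing assumptions.

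**What to change.** Reconcile the quantity dispensed per visit, the visit windows and the handling of collected tablets so that supply covers every permitted interval. State the compliance denominator so that a run-out is identified as such, and say whether the thresholds apply at Visit 7. How this is done is the sponsor's choice.

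The SAP is written in the past tense, so where visits have already taken place, the actual intervals and tablet counts for each woman could be reported beside the results.

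The cost is protocol wording. Planned supply is already 5 × 35 = 175 tablets for at most 147 days, so no additional drug is needed in total.
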